4. HUMAN SUBJECT PROTECTION

Recruitment and Consent Processes:
All potentially eligible childrens' parents will be approached to have their child participate. Primary Care Manager (PCM) referrals, with the patients' parents oral or written authorization, and posted advertisements will be utilized for recruiting children to the study. Some children may be patients of the PI or AI, however, they will have another study staff recruit the children through their parents to prevent any misconception of coercion or undue influence. When a potential child is identified by the treating PCM, their parent(s) will either be provided a contact number to the Research Staff, the Research Staff will be given the potential subjects contact information by the PCM with the parent's oral or written authorization, or the Research Staff will speak with the child's parent(s) directly, if contacted by the parent.

Consent Processes:
Parental Informed Consent (ICD) and HIPAA Authorization (HIPAA) will be sought in advance from each prospective child's parent(s) and appropriately documented in accordance with 32 CFR 219.117. Potential childrens' parents will be notified about the study either through posted advertisements, verbally through their child's primary care manager, or upon check in at the clinic and will be given the opportunity to consent for the child by one of the referred study coordinators. The study coordinator will provide a written copy of the Parental Informed Consent Document and HIPAA Authorization. The potential child's parents may decline to consent for the child without prejudice. At the parent's discretion, they may take the ICD and HIPAA home to discuss further prior to making a decision. If the parent consents to having their child enrolled in the study, a copy of the ICD will be given to them. Each parent will be asked to allow us to include their child's de-identified research data into the "Mike O'Callaghan Military Medical Center General Research Data Repository (FWH20180064H)" for future research.

Recruiting Service Members	Will you be recruiting service members in a group setting?	 Yes	 No
-----------------------------------	--	------------------------------	--

Participation Compensation:

Children and parents will not be paid for participation in this study.

Assent Process:

Parent consent will be acquired via the written consent forms prior to the initiation of any research activities.

Benefits:

There may be decreased levels of urine contamination in either the saline or the iodine prep group's urine sample. If so, this will give a child's treatment team more reliable test results and decrease the need for more invasive urine testing. Additionally the normal saline preparation may be effective at decreasing the level of contamination as the iodine, this is the benefit of using normal saline for a preparation and comparing it to the iodine.

Risks:

Procedure is safe and the only possible negative outcome could be skin irritation from the iodine prep group. There are risks that urine sample may show that there was growth of bacteria on culture in which event the parents will be contacted by the PI or AI and made aware of these results and will be advised to follow up with their pediatrician. There is a possibility that the child has an allergic reaction to the iodine swab. If this occurs, the child will be referred to their pediatric PCM. The urine sample collected during the QW procedure will still be used for the study. There may be a risk of inadvertent breach of confidentiality.

Costs: None

Safeguards for Protecting Information:

Parental Informed Consent and HIPAA authorization will be sought in advance of any screening and study-related procedures for each prospective child participant and appropriately documented in accordance with 32 CFR 219.117. Parents of potential children will be notified about the study either through posted advertisements or through their healthcare provider and parents will be given the opportunity to be consented by one of the referred study coordinators. The study coordinator will provide a written copy of the Informed Consent Document (ICD) to the parent. The parent may decline to consent for their child without prejudice. At the parent's discretion, they may take the ICD home to discuss further with family members or another physician, prior to making a decision. If they decide they are interested in their child participating in the study, they can contact the research department. If the parent consents, a copy of the signed ICD and HIPAA Authorization Document will be given to the parent. Parents who cannot provide Informed Consent on behalf of their child, then the child will not be allowed to participate in the study. No Legally Authorized Representatives (LAR) will be utilized. Each parent will be asked to place their child's de-identified research data into the "Mike O'Callaghan Military Medical Center General Research Data Repository" (FWH20180064H) for future research. If the parent does not give their authorization, then the child's de-identified research data will be destroyed no later than 3 years following the closure of the study.

Data and Specimen Storage Plan**How will coded or identifiable data/specimens be stored?**

	Paper data, including completed consent forms	The research consents and HIPAA Authorization Documents will be stored in a locked cabinet in a locked room with restricted access.
	Electronic data	Medical records will not be annotated to reflect the child's participation in a research study since the child will not receive an invasive research intervention or procedure. All coded, de-identified research data will be electronically stored separately from the Master Key of identifiable patient demographics and PHI/PII.
	Specimens	Urine samples will be disposed of by the lab after analysis is complete. Results will be acquired through CHCS using the child's DoD ID# and name. DoD ID# will be used initially for urinalysis results tracking and then Study code IDs will be used for de-identified research data
	Long-term storage (following completion of the study and inactivation of IRB approval)	The research data will be coded and any links to identifiable data will be destroyed (an approved shredding bin) as soon as possible or no later than at the closure of the study, with the exception of those parents that consented to place their child's de-identified research data into the "Mike O'Callaghan Military Medical Center General Research Data Repository" (FWH20180064H) for future research. The anonymized

		research data will not be utilized for further research activity beyond the protocol stipulations without additional IRB approval. All de-identified research data will be maintained for 3 years following study closure.
--	--	--

Safeguards for Protecting Subjects Relative to Reasonably Expected Risks:

The principal investigator will be responsible for the protocol safety monitoring. The PI will make study documents (e.g., consent forms, data pulls) and pertinent hospital or clinical records readily available for inspection by the 59 MDW IRB and over sight staff for confirmation of the study data. If at any time the parent reports a side effect being experienced by their child, they will be referred to one of the Investigators for care or to the child's pediatric PCM.

Categories of subjects

Children (17 yrs or less), includes viable neonates (28 days of age to 12 months)

Clinical Care:

All children will receive standard of care regardless of inclusion into this study. If at any time a child experiences any injury or adverse effects, appropriate clinical care will be given or the child will be referred to appropriate provider. If a urine sample should be abnormal the PI or AI will follow up with the child's parents and ensure they either follow up with their primary care provider or report to the emergency department, if symptomatic.

Injury Compensation: N/A**Data Safety Monitoring**

N/A – none of the situations listed above apply

5. ALTERNATIVES**Alternatives:**

The alternatives for QW urine collection are urine specimen collection by using the bag specimen collection method or the invasive straight catheterization or suprapubic aspiration. The alternative to using an iodine cleansing solution is to use a normal saline solution. The parents also have the authority to deny their child's participation in the study.

6. DATA ANALYSIS**Data Analysis:**

Primary analysis will be performed by intent-to-treat including all randomized children, where primary outcome data are available, consistent with the CONSORT guidelines for intention to treat analysis. The primary outcome measure is a binary yes/no outcome of detection of microbial markers to determine level of contamination. The absolute difference between the two groups will be reported so that the percentage of contamination samples, together with the 95% CI for the differences of percentages, and calculate p values using a chi squared test. A p value of <0.05 will be considered significant. For the secondary outcome there will also be a measure of binary yes/no outcome of voiding urine within 5 minutes. The rate of successful voiding within 5 min will be described for each group with percentages and 95% CI. The p value will be estimated using chi squared test for categorical variables and t-test or Wilcoxon's rank sum tests for continuous variables.

Additionally we will also be evaluating patient's gender, and age in months for comparative data analysis to help strengthen the study's statistical design outcomes.

Outcome Measures:

Level of urine contamination (binary yes or no), if there was a sample collected in 5 minutes (binary yes or no), and time to void with a 300 second cap are the two outcome measures being evaluated in this study.

Sample Size Estimation/Power Analysis:

This is a pilot study and will have a relatively low sample of 60 subjects.

Statistical Analysis:

Data analysis will be conducted by Baylor University statistics department ([name])

Number of Subjects:	# Planned to Enroll	# Enrolled	# Planned to Complete Study	TOTAL
----------------------------	----------------------------	-------------------	------------------------------------	--------------

Number of Subjects at 99 MDG	60	0	60	60
------------------------------	----	---	----	----

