2. RESEARCH PLAN

Purpose of Study:
The primary aim of this study is to see if the use of an antiseptic preparation (povidone iodine) versus cold normal saline, will decrease rates of urine contamination during the non-invasive Quick Wee (QW) collection of pediatric urine.
Hypotheses, Research Questions, or Objectives:
To evaluate two different cleansing solutions in controlling urine contamination.
Significance
If the use of antiseptic preparation decreases the level of contamination in this study then it would provide an effective and reliable clean catch method that staff could utilize prior to electing for catheterization or suprapubic aspiration.
Military Relevance:
Having a noninvasive Quick Wee method with a high 5 minute void success rate; patient wait times in the emergency department will decrease, and parents will be happier with avoiding invasive measures. This improves patient safety, and provides the clinician with another method for collecting urine. In the Air Force's move towards a culture of safety, and zero harm; further evaluation into this novel technique's reliability will support our goals provided rates of urine contamination can be minimized. The importance of researching noninvasive methods with low levels of contamination is that it may prevent further invasive methods from being used. For example if a child's urine specimen from clean catch is contaminated the next step would be to get the sample via catheterization, a method that is traumatic to child, parent and sometimes staff. If research shows that urogenital prep with iodine decreases level of contamination in the urine then it provides an acceptable method of urine clean catch collection.
Background and Review of Literature:
Urinary tract infections (UTI) are common acute illnesses among pediatric patients, accounting for 5-7% of emergency department visits in the under two-year-old population [1]. However, obtaining urine samples from the precontinent patient can be difficult. There is an ongoing debate regarding which noninvasive method for urine specimen collection is best for this population. The main argument against clean catch is the high rate of contamination compared to invasive collection and reliability.

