There are many methods of noninvasive urine collection. These methods are preferred as they are fairly well tolerated by patients, less distressing to parents, cost effective, and require less technical expertise. In the past; these methods have been dismissed due to their high rates of contamination, time to void and also effectiveness. The National Institute of Health and Clinical Excellence (NICE, UK) recommends a clean-catch urine (CCU) be the first attempt at obtaining a urine specimen from children suspected of having UTI [2]. This means placing the urine specimen collection container into the urine mid-stream once the child has begun to void to avoid contamination. Conversely, the American Academy of Pediatrics recommends clean

catch urine for screening and a catheter specimen urine collection or suprapubic aspiration for definitive diagnosis [3]. Both of these invasive techniques produce quick urine samples with low rates of contamination; however they can be painful and distressing to both the patient and parent.

The Quick-Wee method for noninvasive urine collection has been evaluated in a one randomized controlled trial and has been shown to significantly increase the five minute voiding success rate for CC urine collection; 31%, n= 174. However a past study demonstrated contamination rate of 27%, n=174. No study has directly evaluated the use of antiseptic solution in the evaluation of the QW rate of contamination in pediatric patients. The purpose of this study is to see whether the use of povidone iodine swabs prior to the QW method will decrease the rate of contamination. A decrease of the rate of contamination would strengthen the validity of this simple CCU method. Also using the this method for the collection method in both the experimental and control groups will further evaluated the five min void success rate.

We chose to use iodine as our prepping agent because it is currently the standard cleaning solution used for adult and pediatric patients. It is readily available, inexpensive and has been shown to be less caustic then other prepping agents.

Bibliography:

1. Shaw, K. N., Gorelick, M., McGowan, K. L., Yakscoe, N. M., & Schwartz, J. S. (1998). Prevalence of urinary tract infection in febrile young children in the emergency department. *Pediatrics*, *102*(2), e16-e16.

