3. RESEARCH DESIGN AND METHODS

Research Design and Methods:

Male and Female DoD beneficiaries, aged one month (28 days) to 12 months (365 days), meeting the inclusion/exclusion criteria will be offered an opportunity to participate. Each child will already be scheduled for a standard of care urinalysis collection procedure through their pediatric PCM. They will be recruited from the clinics located at the 99MDG through direct contact with the infant’s parents. All of the below items are research-related unless marked as ‘standard of care’:

The study will be a non-blinded randomized controlled trial with parallel assignment of groups, taking place in the pediatric and emergency departments. The subject’s parents will be asked if the patient has had an allergic reaction to iodine in the past prior to being placed in experimental group and if they have had a reaction in the past they will be placed in the normal saline group instead. Additionally, if the patient develops a reaction to iodine during testing then they will have the region cleansed with normal saline, will be evaluated by the medical staff performing the test, then the urine and subject’s data will be disposed of and excluded from the study. The experimental group will have their periurethral region cleansed with povidone iodine solution while the control group will be prepped with cold (2°C) normal saline. Both groups will have the urine collection performed utilizing the QW method (see attached flow chart). If a sample is not collected within five minutes with the QW method it will be documented as a failure and the child will be referred back to their pediatric PCM and removed from the study. Urine collection will occur at the hospital.

Utilizing sequentially numbered opaque sealed envelopes (SNOSE), children will be randomly assigned to one of the two treatment groups. The envelopes will contain plastic forceps, gauze, and a 3x5 index card listing the group the child has been assigned, i.e., iodine or normal saline, as well as child’s ID number; For the experimental group there will be a package of iodine swabs and the control will have a normal saline flush. Also contained within the envelope will be the Participant Data Sheet to provide an easy way to track the urine collection process for the study..

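### The primary analysis is labelled intent-to-treat but compares tested samples only, with no accounting by arm for children without a result and conflicting rules for children who react to iodine

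*Combined protocol and SAP*

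**What the plan says.** Section 6, Data Analysis, defines the primary population: "Primary analysis will be performed by intent-to-treat including all randomized children, where primary outcome data are available". It adds that this follows CONSORT. The measure is "the percentage of contamination samples, together with the 95% CI for the differences of percentages", so the denominator is samples. Voiding within five minutes is a separate yes/no outcome, reported by arm. Time to void is capped at 300 seconds.

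Section 3 determines who can have a contamination result. The data sheet records time to void, whether urine was caught, and later the laboratory finding. If there is no sample in five minutes, "it will be documented as a failure and the child will be referred back to their pediatric PCM and removed from the study".

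On a reaction to iodine during the procedure, Section 3 says that the urine and the child's "data will be disposed of and excluded from the study". The Risks paragraph of Section 4 says the opposite about the specimen: when a child reacts, the urine collected remains in use for the study.

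The Background in Section 2 cites earlier work on the method: "voiding success rate for CC urine collection; 31%, n= 174. However a past study demonstrated contamination rate of 27%, n=174".

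**The concern.** An intent-to-treat label tells the reader that the randomised groups are compared whole. Here a child enters the primary comparison only after cleansing, a void in time, a successful catch and a laboratory result. Each of these follows randomisation in an unblinded trial. The plan has no rule for children who fall out along the way and does not commit to counting them by arm. A reader of the result could not see how far the two compared sets depart from the two randomised groups.

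The stated use of the method makes the denominator matter. If contamination falls, Section 2 says, "it would provide an effective and reliable clean catch method that staff could utilize prior to electing for catheterization". For that use, a clinician also wants to know how many children attempted yield an uncontaminated sample. Contamination and voiding are each planned by arm, but no planned analysis combines them.

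The reaction rule is a separate matter and a direct contradiction. Only children in the iodine arm are exposed to iodine, so discarding data after a reaction removes children from one arm, after randomisation and for a reason caused by the intervention. That cannot stand beside a statement that all randomised children with outcome data are analysed.

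**Working it through.** **Who is in the primary comparison**

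| Child's course | Contamination result? | In primary comparison? |
|---|---|---|
| No void in five minutes | No | No |
| Void, urine not caught | No | No |
| Caught, no laboratory result | No | No |
| Caught and tested, no reaction | Yes | Yes |
| Caught and tested, reaction to iodine | Yes | No under Section 3; yes under Section 4, Risks |

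**How many children that might be.** The total of 60 comes from Section 6, which gives no derivation to reproduce. The 31% comes from Section 2. It is a background voiding rate, not a design assumption. Missed catches and absent laboratory results would put sample success below the voiding rate. The local rate is unknown, so I show a range: expected number = 60 × success rate.

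- 31%: 60 × 0.31 = 18.6. The binomial 95% range for 60 children is 12 to 26.
- 50%: 60 × 0.50 = 30.
- 70%: 60 × 0.70 = 42.

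At 31%, 1 − 0.31 = 69% of randomised children would be outside the comparison.

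**The two denominators can disagree (illustration).** Uncontaminated samples per child randomised = success × (1 − contamination). Suppose that saline has the cited 31% and 27%, and that 27% is per collected sample: 0.31 × 0.73 = 22.6%. Suppose iodine halves contamination to 13.5%. It then gives no gain per child if its success rate is 0.2263 / 0.865 = 26.2%, and a loss below that. Nothing in the documents says that success will differ by arm. The example shows only that contamination among samples does not settle yield per child.

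**Precision of a per-child comparison (illustration).** Assume 30 per arm, 31% success in both arms, and contamination of 27% with saline and 10% with iodine. The yields are 0.31 × 0.73 = 22.6% and 0.31 × 0.90 = 27.9%. The 95% half-width is 1.96 × √(0.2263 × 0.7737/30 + 0.279 × 0.721/30) = 0.219, about 22 points. The exact power of the uncorrected chi-squared test is 0.074.

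**What one discarded child can do (illustration; the documents give no reaction rate).** With 2 of 9 iodine samples contaminated, the rate is 22.2%. Discarding one contaminated sample gives 1/8 = 12.5%, a shift of −9.7 points. Discarding one uncontaminated sample gives 2/8 = 25.0%, a shift of +2.8 points.

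**The case against.** Much of the case on the other side stands.

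- **The restriction is not hidden.** The sentence that claims intent-to-treat also limits the set to children with outcome data. The stated aim concerns contamination, and contamination among samples is a proper primary question. Whether the wording departs from CONSORT cannot be judged from these documents, and the point does not rest on it.
- **A reader might infer a material bias.** The documents do not show one. Both arms receive the same five-minute cold stimulus, so differential loss may be small. It cannot be ruled out either: the control cleansing is itself cold, and no temperature is given for the iodine.
- **A reader might take the small number of samples as evidence of bias.** At 27% contamination in both arms and a 1:1 split, 1.96 × √(2 × 0.27 × 0.73/m) is about 40 points at m = 9.3 per arm and 22 at m = 30. That is imprecision in a declared pilot, not bias from the analysis set.
- **A reader might set the 60 under "Planned to Complete Study" against the 31% and conclude that the plan expects 60 samples.** The table does not say so. A child who undergoes the attempt and is recorded as a failure supplies the voiding outcome and can be counted as completing.
- **A reader might conclude that failures are lost to all analyses.** The yes/no voiding outcome and the 300-second cap make sense only if failures keep their data. The wording on removal is loose, but the intention can be inferred.
- **A reader might call the per-child composite the only comparison that keeps the randomised groups whole.** It is not. Contaminated samples per child randomised, or best- and worst-case analyses, would also do so. The composite can also be rebuilt from arm counts if those are reported. What is missing is pre-specification and a commitment to the counts.

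The reaction conflict survives these objections. Section 3 refers to reactions during testing and the Risks text gives no timing, but that difference does not clearly reconcile them.

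**Conclusion.** The point holds in two parts.

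First, the primary analysis is an available-case comparison by randomised group, conditional on a caught and tested sample. It is mislabelled, and nothing commits the sponsor to account by arm for children without a result. The share outside the comparison could be large: about 41 of 60 if sample success were near 31% (60 − 18.6 = 41.4), 30 at 50%, and 18 at 70%. These figures rest on an unknown local success rate. The direction and size of any bias are unknown.

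Second, the rule for children who react to iodine is contradictory between Sections 3 and 4. As written in Section 3, it also contradicts Section 6 and can act on the iodine arm only. This part needs no numerical assumption.

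The changes should be made before analysis. They do not call for a different primary question.

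**What to change.** 1. Reconcile Section 3, the Risks text in Section 4 and Section 6 on whether data from children who react to iodine are analysed. State one analysis-set rule consistent with analysis by randomised group, and report any exclusion by arm. This concerns data handling only, not the care of the child.
2. In Section 6, describe the primary set as available-case by randomised group, conditional on a sample within five minutes. Report children without a result per arm by reason: no void, missed catch, no laboratory result, excluded after a reaction.
3. Add one descriptive supportive 2×2 comparison over all randomised children, *uncontaminated sample obtained within five minutes*, with the difference and 95% CI. No void, a missed catch or a contaminated sample counts as no. Keep contamination among samples as primary.
4. State that removal from the study after a failed collection does not remove the child from the voiding analysis.

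The cost is a few sentences and one table, built from void time, catch and contamination, which Section 3 already has recorded. The downside is in item 3: the composite mixes voiding with contamination, dilutes a pure contamination effect and is imprecise, as the half-width of about 22 points shows. It should therefore stay descriptive.

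### Sixty children are planned to complete, but only those with urine caught within five minutes (about 19 of 60 at the protocol's own 31%) can supply the primary outcome

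*Combined protocol and SAP*

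**What the plan says.** All references are to the combined protocol and SAP.

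- **Size.** Section 6, Sample Size Estimation, calls the study a pilot of 60 and gives no effect size or power. The Number of Subjects table shows 60 to be enrolled and 60 to complete.
- **Primary analysis.** Section 6, Data Analysis, calls it intent-to-treat, "including all randomized children, where primary outcome data are available". The outcome is binary contamination.
- **No sample.** Section 3, Research Design and Methods, gives the rule for a child from whom no urine has been obtained when the five minutes are up: "it will be documented as a failure and the child will be referred back to their pediatric PCM and removed from the study". The same section has staff record time to void, whether the urine was caught in the cup, and later the laboratory's contamination result.
- **Secondary outcomes.** Section 6, Data Analysis, uses a "binary yes/no outcome of voiding urine within 5 minutes". Section 6, Outcome Measures, lists instead whether a sample was collected in five minutes, together with time to void capped at 300 seconds. Section 3, Interventions and Observations, describes success in providing a clean-catch urine within five minutes.
- **Expected success.** Section 2, Background, says that the method was shown to "increase the five minute voiding success rate for CC urine collection; 31%, n= 174". Section 2, Military Relevance, is more hopeful but gives no number: "Having a noninvasive Quick Wee method with a high 5 minute void success rate".

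**The concern.** Contamination is a property of a urine sample, so a child without a sample has no primary outcome. The absence is not occasional missing data. It follows from how the procedure works, and at the document's own rate it affects most children. The plan nevertheless gives 60 as its only size and uses a label that usually means everyone randomised is analysed. A reader would take the contamination comparison to be about three times as large as it is likely to be, and would not see that its groups are formed after randomisation.

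The removal wording raises a second matter. The five-minute success rate needs the failures in its denominator, and time to void needs them as the values at the 300-second cap. If staff apply the removal literally, both outcomes lose the children who give them meaning. A void that misses the cup adds a third: it is a success under one of the stated definitions and a failure under the others.

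**Working it through.** **Inputs**

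- Planned number: 60 (section 6).
- Five-minute success rate: 31% (section 2, Background), the only number given for it.
- Sensitivity rates: 25% and 50%. Both are assumptions, not taken from the document.
- Allocation: the ratio is not stated, so 1:1 is assumed for per-arm figures.

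**The plan's own figure.** The 60 cannot be reproduced, because no effect size, power or success rate is attached to it. It can only be compared with what the procedure would deliver.

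**Expected number with a contamination result** = 60 × success rate, with the 2.5th and 97.5th percentiles of a binomial with n = 60:

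| Success rate | Expected | 95% binomial range | No primary outcome (expected) |
|---|---|---|---|
| 25% (assumed) | 60 × 0.25 = 15.0 | 9 to 22 | 60 − 15.0 = 45.0 |
| 31% (section 2) | 60 × 0.31 = 18.6 | 12 to 26 | 60 − 18.6 = 41.4 |
| 50% (assumed) | 60 × 0.50 = 30.0 | 22 to 38 | 60 − 30.0 = 30.0 |

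At 31% this is 18.6 / 2 = 9.3 children per arm. The ranges reflect chance at a fixed rate, not uncertainty about the rate itself.

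**If 31% counts voids and not catches**, the number is lower. With 90% or 80% of voids caught (assumptions), 18.6 × 0.9 = 16.7 and 18.6 × 0.8 = 14.9.

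**How firm is 31%?** The same paragraph adds: "However a past study demonstrated contamination rate of 27%, n=174". If both percentages were plain proportions of the same 174 children, then 0.31 × 174 = 54 would have succeeded and 0.27 × 174 = 47 would be contaminated, that is 47 / 54 = 87% of samples. That does not fit a contamination rate of 27%, so at least one denominator is probably not as printed. The 31% can anchor an expectation, but the n of 174 should not be used to put confidence limits on it.

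**Literal removal of failures.** If every child without a sample leaves the data, all who remain have voided within five minutes. The rate is voids / voids = 100% in both arms, and no child contributes a value at the 300-second cap.

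**A void that is not caught, under each definition**

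| Place | Event scored | Void not caught counts as |
|---|---|---|
| Section 6, Data Analysis | Voiding within 5 minutes | Success |
| Section 6, Outcome Measures | Sample collected in 5 minutes | Failure |
| Section 3, Research Design and Methods | Sample collected within 5 minutes | Failure |
| Section 3, Interventions and Observations | Clean-catch urine provided in 5 minutes | Failure |

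The conflict therefore lies within section 6 as well as between sections 3 and 6.

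**The case against.** The best defence is that the plan discloses the restriction: "including all randomized children, where primary outcome data are available" already limits the analysis to children with a result. A reader might infer that the protocol promises 60 contamination results. It does not. A documented failure may well count as having completed, and the table entry may be purely administrative. This stands, and it reduces the matter to an unstated number and a misleading label.

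The 31% is also soft, and section 2 elsewhere expects a high rate. That stands too, and is why a range is needed. Even at an assumed 50%, half the children supply no primary outcome.

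A reader might infer that the failures' data will be lost. The natural reading is that they are kept: they are to be recorded as failures, and a 300-second cap makes little sense without them. In section 3, disposal is ordered only after an iodine reaction, where the subject's "data will be disposed of and excluded from the study". (Section 4, Risks, says that the sample is still used in that case; those two passages need reconciling separately.) The removal wording thus calls for clarification and does not show that the secondary outcomes are void.

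Most of the per-arm counts already follow from planned outcomes, since voiding is reported by group and catching is recorded. What is missing is the instruction to set them beside the primary comparison.

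Finally, a reader might infer bias, because the analysed groups are selected after randomisation. The document does not show it. Both arms receive the same five-minute stimulation and differ only in a ten-second cleanse, so differential success is possible but not demonstrated.

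**Conclusion.** The point holds as a reporting and labelling defect. The stated 60 is not the size of the primary comparison. That comparison is expected to rest on about 19 children at 31%, or 15 to 30 over the assumed rates of 25% to 50%. It is an available-case comparison conditional on a caught sample, not intent-to-treat as usually understood. These figures assume that one loosely worded rate, or the assumed alternatives, applies here and that failures are not replaced; the document mentions no replacement.

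Two smaller matters stand with it: the removal wording must be reconciled with the secondary outcomes, and voided or caught must be settled for the five-minute outcome.

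It would be tempting to conclude that the sample size calculation is wrong or the trial underpowered. The document does not support that. It calls itself a pilot, makes no power claim and names no target difference, so there is no such claim to contradict. The point should be fixed, but it does not invalidate the design.

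**What to change.** 1. **Section 6, Sample Size Estimation and Number of Subjects.** State that 60 are randomised and that about 19 are expected to supply the primary outcome at 31%, with 15 at an assumed 25% and 30 at an assumed 50%. Label the numbers as assumption-based.
2. **Section 6, Data Analysis.** Describe the primary comparison as an available-case comparison between the randomised groups, conditional on a sample caught within five minutes. Show the randomised, voided and caught counts per arm beside it.
3. **Sections 3 and 6.** State that documented failures stay in the denominator for five-minute success and in the time-to-void analysis. Choose one definition, voided or caught, for the secondary outcome and use it throughout. This concerns data handling only; the referral of the child is not affected.

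The cost is a few sentences and one count table from data that staff already record. The primary comparison, the chi-squared test and data collection are unchanged. The downside is that the completer figure will look less favourable and that the expected number, resting on one uncertain rate, must be given as a range.
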